5.1 Method of Assigning Subjects to Treatment Groups

Subjects will be randomly assigned in a 1:1:1:1 ratio to receive SKI-O-703 100 mg BID, 200 mg BID, 400 mg BID, or matching placebo. An interactive voice or web response system (IxRS) will be used to administer the randomization schedule. The randomization schedule will be generated using SAS software version 9.3 or later (SAS Institute Inc., Cary, North Carolina) for IxRS, which will link sequential subject randomization numbers to treatment codes. The randomization schedule will be stratified by prior anti-TNF α biologic agents use (Yes or No), the number of previous csDMARDs treatments (0~2 or ≥ 3), specific geographic region (APAC, EMEA, and NA), and PK/PD sampling (Yes or No). It will also use an appropriate block size, which will not be revealed.

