7.7 Statistical Analysis Methodology

Statistical analysis will be performed using SAS® software Version 9.3 or later. The results for each efficacy endpoint will be summarized by visit and treatment for all subjects within the ITT, mITT, and PP sets using descriptive statistical methods. Continuous variables will be summarized using the mean, SD, median, minimum value, and maximum value. Categorical variables will be summarized using frequency counts and percentages. Data will be listed in data listings.

Further details of the statistical analyses, methods, and data conventions will be described in the statistical analysis plan.

All statistical tests will be 2-sided and performed using a 5% significance level, leading to 95% CIs (2-sided). There will be no adjustments for multiplicity.

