7.7.3 Analysis of Primary Endpoint

The primary endpoint is the mean change from baseline in DAS28-hsCRP at Week 12 which is based on 3 individual components including TJC, SJC and hsCRP (see calculation in Appendix 13.6).

The mean change from baseline in DAS28-hsCRP at Week 12 between each of the active treatment groups and the placebo arm will be analyzed using an analysis of covariance (ANCOVA). The difference in mean change from baseline between each active treatment and the placebo will be estimated and the corresponding 95% CI and p-value will be calculated.

The primary endpoint will be analyzed using the ITT, mITT, and PP analysis sets. For the mITT set, results for subjects that are missing at Week 12 will be imputed using the last observation carried forward (LOCF) method.

A sensitivity analysis based on the 4-component DAS28-hsCRP (consisting of 4 individual components including TJC, SJC, hsCRP, and subject's global assessment of disease activity [VAS]; see calculation in Appendix 13.6) will be performed on the ITT set restricted to subjects who consistently completed the subject's global assessment of disease activity reverse VAS scale.

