7.7.4 Analysis of Secondary Endpoints

For secondary endpoints, change from baseline will be analyzed at Weeks 2, 4, 8, and 12 using a mixed model repeated measures (MMRM) analysis. The Chi-square tests will be used to compare the ACR20, ACR50, and ACR70 rates between the active treatment and placebo groups at Weeks 2, 4, 8, and 12. The median hsCRP will be summarized descriptively.

The DAS28-related secondary endpoint is based on 3 individual components including TJC, SJC and hsCRP (see calculation in Appendix 13.6). Sensitivity analyses based on the 4-component DAS28-hsCRP (consisting of 4 individual components including TJC, SJC, hsCRP, and subject's global assessment of disease activity [VAS]; see calculation in Appendix 13.6) will be performed using the ITT set restricted to subjects who consistently completed the subject's global assessment of disease activity reverse VAS scale.

All secondary endpoints will be analyzed using the ITT and PP analysis sets. The ACR20, ACR50, and ACR70 will be also analyzed using the mITT set, where results for subjects that are missing at the relevant visit will be imputed using nonresponder imputation (NRI).

For analyses on ACR responses (ACR20, ACR50 and ACR70) described above, the analysis will be performed on the subjects assessment of arthritis pain and physician global assessment of disease activity VAS scales, using the same approach as the sensitivity analysis on 4-component DAS28-hsCRP to identify the subjects to be included in this analysis set.

For the analyses on the other VAS-related secondary endpoints (ie, the individual assessments using VAS), using the same approach as the sensitivity analysis on 4-component DAS28-hsCRP, only subjects who completed the corresponding individual VAS assessment consistently will be included.

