4.3. Sample Size

Approximately 148 subjects will be enrolled in 4 cohorts (3 cohorts of SKI-O-703 and 1 cohort of placebo). Each cohort will consist of at least 37 subjects.

The study is powered to detect a difference of 0.8 in mean change from baseline to Week 12 in DAS28-hsCRP score between one of the groups treated with SKI-O-703 and the group treated with placebo. At least 37 subjects on a course of SKI-O-703 treatment are required to complete the study to show a change from baseline to Week 12 of 0.80 and higher as statistically significant with a power of 0.80 at the significance level of 0.05, using a 1-way analysis of variance and assuming a standard deviation of 1.25, compared with in the placebo group. Sample size determinations were based on the 4-component DAS28 and are likely to be similar with the 3-component DAS28 with fewer variables.

Given the 1:1:1:1 ratio of SKI-O-703 100 mg BID, 200 mg BID, 400 mg BID to placebo allocation, at least 37 subjects in each treatment group are required to complete the study, therefore at least 148 subjects need to be enrolled and randomized in the study. Assuming a drop-out of rate of 10%, up to 20 additional subjects may be enrolled to achieve the target number of subjects required to complete the study.

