4.4. Randomization, Stratification, and Blinding

Subjects will be randomized using a permuted block randomization in parallel in a 1:1:1:1 ratio (37 subjects per group) to receive SKI-O-703 100 mg BID, 200 mg BID, 400 mg BID, or matching placebo. An interactive voice or web response system (IxRS) will be used to administer the randomization schedule. The randomization schedule will be stratified by prior anti-TNF α biologic agents use (Yes or No), number of previous csDMARDs treatments (0-2, ≥ 3), and specific geographic region (APAC, EMEA and NA).

This study is double-blind study. Neither the subjects nor the investigator will be aware of the treatment assignment for the subjects in each cohort. The study drugs will be similar in number and appearance for each cohort to maintain the study blind. Blinding will be maintained throughout the study until the final database lock.

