8.2.1. Primary Analysis

The primary analysis will be conducted on observed cases, which means DAS28-hsCRP at Week 12 will be calculated only when all the three individual components (TJC28, SJC28 and hsCRP) are assessed at this visit; otherwise, DAS28-hsCRP at Week 12 will be considered as missing.

The change from baseline in DAS28-hsCRP at visit Week 12 will be analyzed using an analysis of covariance (ANCOVA) model. The model will include treatment groups as a factor and DAS28-hsCRP at baseline as a covariate. Within-group least-square (LS) means and the associated standard errors (SE), the treatment differences in LS means and the associated SEs, the 2-sided 95% CIs, the 2-sided p-values for treatment comparisons between each of active treatment group and placebo group, and the 2-sided p-values for treatment comparisons among active treatment groups (high dose vs. low dose) will be estimated and provided. Descriptive statistics of baseline, observed value and change from baseline at Week 12 will be summarized by treatment group.

The primary efficacy analyses will be performed based on the ITT set, and then repeated using the PP set.

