For all other secondary efficacy endpoints, descriptive statistics of baseline, observed value and change from baseline at each schedule visit will be provided by treatment group. Treatment comparisons will be conducted using a mixed model repeated measure (MMRM) analysis, including all the scheduled visits up through Week 12. The model will be fitted with treatment group, visit, treatment by visit interaction and baseline as fixed effects, and visit within subject as a repeated effect, using an unstructured covariance to model the between- and within-subject errors. If the model fails to converge with unstructured covariance matrix, use the heterogeneous Toeplitz covariance structure, followed by the heterogeneous autoregressive covariance, followed by the compound symmetry covariance structure. The inferential statistics from this model, including within-group LS means and the associated SE, treatment differences in LS means and the associated SEs, the 2-sided 95% CIs, the 2-sided p-values for treatment comparisons between each of active treatment group and placebo, and the 2-sided p-values for treatment comparisons among different active treatment groups (high dose vs. low dose) will be provided.

Listings for ACR responses, DAS28-hsCRP assessments, number of tender and swollen joints, subject assessment of pain using VAS, subject and physician global assessment of disease activity and HAQ-DI will be provided.

Plots of LS mean change from baseline in continuous primary and secondary efficacy endpoints by visit will be provided as well. Proportion of subjects with ACR response will be plotted by visit.

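### Free improvement: the primary ANCOVA and the MMRM leave out the factors that randomisation is stratified by, so the test is conservative if those factors predict Week 12 change

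*SAP*

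**What the plan says.** **Randomisation.** SAP 4.4 describes permuted blocks, 1:1:1:1, stratified by prior anti-TNF use (yes/no), number of previous csDMARDs (0-2, 3 or more), "and specific geographic region (APAC, EMEA and NA"). Protocol 5.1 lists the same three factors and a fourth: "and PK/PD sampling (Yes or No"). That is 2 × 2 × 3 = 12 strata in the SAP and 24 in the protocol. SAP section 14 reports no changes from the planned analysis.

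**Primary model.** Protocol 7.7.3 says only that the change "between each of the active treatment groups and the placebo arm will be analyzed using an analysis of covariance (ANCOVA"), without naming covariates. SAP 8.2.1 fills this in: "The model will include treatment groups as a factor and DAS28-hsCRP at baseline as a covariate".

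**Secondary continuous endpoints.** SAP 8.3.1: "The model will be fitted with treatment group, visit, treatment by visit interaction and baseline as fixed effects". Protocol 7.7.4 names an MMRM without listing its terms.

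**ACR responses.** Protocol 7.7.4: "The Chi-square tests will be used to compare the ACR20, ACR50, and ACR70 rates between the active treatment and placebo groups".

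**Where the strata are used.** They enter the multiple-imputation regression (SAP 8.2.3) and define the subgroups (SAP 8.5; Protocol 7.6). The imputed data are then analysed with the primary model, which drops them. No reason is given for leaving them out.

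**The concern.** Stratified blocks balance the strata across arms, so any outcome variation due to the strata largely cancels from the difference between arms. A model without the strata does not know this and counts that variation as residual error. If the strata matter, the reported standard error exceeds the true variability of the estimate, the confidence interval is too wide, and the test rejects less often than 5% under the null.

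What is at stake is precision on the primary endpoint, in a trial whose dose-versus-placebo power is a little below 80% at the stated assumptions. The sponsor evidently thought these factors might matter, since it stratified on them, imputes with them and plans subgroups by them.

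**Working it through.** **Inputs from the documents.** Difference 0.8 in one active arm and SD 1.25, "using a 1-way analysis of variance and assuming a standard deviation of 1.25"; 37 completers per arm; 10% dropout with up to 20 extra subjects (SAP 4.3). "All statistical tests will be 2-sided and performed using a 5% significance level" (Protocol 7.7), with no multiplicity adjustment. About 30% with prior biologic therapy (Protocol 3.1).

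**Assumed, not in the documents.** R², the share of variance left after baseline that the strata explain, is shown over 0 to 20%. SD 1.25 is taken as the SD after baseline. Main simulation: 30% with 3 or more csDMARDs, regions 20/60/20, PK/PD sampling 20%, blocks of 4, and the three SAP factors sharing R² equally.

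**Step 1: the plan's own figure.** For a four-group F-test with means 0, 0, 0, 0.8 the sum of squared deviations is 3 × 0.2² + 0.6² = 0.48, so λ = 37 × 0.48 / 1.25² = 11.4. Power is 80.6% at 37 per arm and 79.4% at 36. The stated 37 is reproduced, without covariates. For one dose against placebo with the pooled error term, power at 37 is 78.1%. Dropout: 148 / 0.90 gives 165, covered by 148 + 20 = 168.

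**Step 2: limiting case, strata perfectly balanced (normal approximation, n = 37).** The true SE is 1.25 √(1 − R²) √(2/37); the planned model reports about 1.25 √(2/37) = 0.291.
- Type I error, planned: 2[1 − Φ(1.96 / √(1 − R²))].
- Power, planned: 1 − Φ[(1.96 × 1.25 − 0.8/√(2/37)) / (1.25 √(1 − R²))].
- Power, adjusted: the usual formula with SD 1.25 √(1 − R²).

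| R² | Type I, planned | Power, planned | Power, adjusted |
|---|---|---|---|
| 0 | 5.0% | 78.6% | 78.6% |
| 5% | 4.4% | 79.2% | 80.6% |
| 10% | 3.9% | 79.8% | 82.7% |
| 20% | 2.8% | 81.2% | 86.8% |

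**Step 3: simulation with realistic imbalance.** 24 strata, 168 randomised, 20 lost at random; 8,000 null and 8,000 alternative replicates per R². 95% Monte Carlo error is about 0.5 points for type I error and 0.9 for power.

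| R² | Type I, planned | Type I, adjusted | Planned model SE / true SD | Power, planned | Power, adjusted | Difference |
|---|---|---|---|---|---|---|
| 0 | 5.3% | 5.2% | 0.99 | 77.3% | 77.1% | −0.2 |
| 5% | 4.6% | 5.0% | 1.02 | 77.9% | 79.7% | +1.8 |
| 10% | 4.1% | 4.9% | 1.05 | 78.7% | 81.7% | +3.0 |
| 20% | 3.4% | 5.1% | 1.08 | 79.6% | 86.4% | +6.8 |

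**Step 4: robustness.** Change in power from adjusting, in points, at R² 0 / 5 / 10 / 20%:
- 148 completers: −0.2 / +1.5 / +2.8 / +6.3
- 148 randomised, 10% lost: −0.4 / +1.4 / +3.4 / +6.7
- blocks of 8: −0.2 / +1.5 / +2.3 / +6.7
- 12 strata, no PK/PD factor: −0.3 / +1.1 / +3.5 / +6.3
- more even splits (5% not run): −0.1 / – / +3.6 / +5.9
- second simulation (35% with 3 or more csDMARDs, 12 strata, 148 analysed): −0.2 / +1.6 / +2.9 / +6.6. At R² 20% the planned model's mean SE is 0.292 against a true SD of 0.261, about 12% too large, and its type I error is 3.0%
- third simulation, same design as Step 3: −0.8 / +0.8 / +3.4 / +5.7. Planned type I error is about 3.7% at R² 20%

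**Step 5: ACR.** Chi-square with 148 subjects and an assumed 30% response in every arm: type I error 4.9 / 4.9 / 4.6 / 4.0%. A Cochran-Mantel-Haenszel test gives 4.8 / 5.2 / 5.2 / 5.1%. Little is at stake there.

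**Step 6: cost.** Error df are 148 − 4 − 1 = 143 as planned. Anti-TNF (1), csDMARD count (1) and region (2) take 4, leaving 139.

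**The case against.** The strongest reply is that nothing is wrong. The sample size assumed no covariates, the protocol promises only an ANCOVA, and the SAP already goes further by adjusting for baseline. The planned test's power does not fall as R² rises (77.3% to 79.6% in Step 3), so a gain is forgone rather than something lost relative to the design. R² is unknown, no passage shows that the strata predict change beyond baseline, and a gain of 6 points or so needs R² of 20%. The 1.25 is also stated for a model without covariates. If baseline explained 10 or 20% of the variance, dose-versus-placebo power at 37 per arm would already be about 82 or 86%, and the gain at R² 5% would be about 1.8 or 1.6 points rather than 2.0 by the same formula.

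All of that is fair, and it makes this an efficiency point rather than an error. It does not argue against the change: adjusting costs under one point of power in every run at R² 0 and gains in every run at R² 5% or more.

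Two practical objections stand as refinements. Main effects in the MMRM force one stratum effect across all visits. A rough check (40 runs only, R² 20%, effect rising linearly to Week 12, within-subject correlation 0.6) gave a Week 12 SE of 0.289 unadjusted, 0.266 with main effects and 0.257 with stratum-by-visit terms. And SAP 8.5 refits the MMRM within subgroups defined by these same factors, where the defining factor is constant.

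**Conclusion.** The concern holds as a conditional efficiency point. Both models omit the randomisation strata without a stated reason. Over all simulations, adjusting changes ANCOVA power by −0.8 to 0.0 points at R² 0, +0.8 to +1.8 at 5%, +2.3 to +3.6 at 10% and +5.7 to +6.8 at 20%. At R² 20% the planned test runs at about 3.0 to 3.7% instead of 5%.

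These figures rest on an assumed R², assumed stratum proportions (apart from the 30% anti-TNF share), an assumed block size, and 1.25 as the SD after baseline. The direction does not depend on these choices; the size does. For the MMRM there is only the rough check above, so the figures should not be carried over to it. Confidence in the size is medium.

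The difference between three and four stratification factors is a separate documentary inconsistency that needs resolving whatever R² is.

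**What to change.** Before database lock:

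1. In SAP 8.2.1 and 8.3.1, add prior anti-TNF use (yes/no), csDMARD count (0-2, 3 or more) and region (APAC, EMEA, NA) as main effects, using the values recorded in IxRS at randomisation. For the MMRM, consider stratum-by-visit terms.
2. Reconcile SAP 4.4 with Protocol 5.1 against the IxRS specification. State whether PK/PD sampling enters the models, and why.
3. State in advance how sparse levels are collapsed or dropped, as SAP 8.2.3 already does for imputation, and that a factor is dropped from the model within its own subgroup (SAP 8.5).
4. Keep the ACR chi-square. A Cochran-Mantel-Haenszel test with a pre-stated pooling rule is optional, mainly for consistency.

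The cost is SAP wording, one model statement for each analysis, and 4 degrees of freedom. Protocol 7.7.3 and 7.7.4 name the methods without listing model terms, so the model changes need no protocol amendment.

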8.2.2. Sensitivity Analysis: Using LOCF

The primary analysis will be repeated based on the mITT set, and the missing value of DAS28-hsCRP at Week 12 will be imputed using the LOCF method. Before calculating DAS28-hsCRP at Week 12, the component-level imputation using LOCF at Week 12 will be performed for each individual component (TJC28, SJC28 and hsCRP).

8.2.3. Sensitivity Analysis: Using MI Under MAR Framework

Repeat the primary analysis on the ITT set and before calculating the DAS28-hsCRP, the missing value of each individual component (TJC28, SJC28 and hsCRP) will be imputed by multiple imputation (MI) method for all treatment groups as described below, under the missing at random (MAR) framework.

The SAS procedure MI will be used to impute the missing value for each individual component at the scheduled post-baseline analysis visits (up to Week 12) to create 25 complete data sets. The missing data patterns will be checked by treatment and at scheduled visits. If there are non-monotone missing patterns, two separate imputation procedures as described below will be used to complete the imputation process; otherwise, skip the first step. For components SJC28 and TJC28, the imputed values will be rounded to integers. The range of imputed value should be from minimum value 0 to maximum value 28 for SJC28 and TJC28. The minimum value for hsCRP should be 0.

In the first step, the Markov Chain Monte Carlo (MCMC) method will be used to impute missing values by treatment to create 25 imputed data sets with monotone missing patterns. The seed will be set to 7032101 and a single chain will be used to procedure imputations.

In the second step, the monotone regression method will be used to impute the remaining missing values for the 25 data sets with monotone missing patterns. The MONOTONE REG statement will be used with the seed 2101703. The missing values at each visit will be imputed based on treatment, stratification factors (prior anti-TNF α biologic agents use, number of

previous csDMARDs treatments, geographic region) and values at baseline and previous visits. (If the imputation cannot be implemented due to lack of sufficient subjects in a specific stratum, remove the factor from the imputation model.)

After the completion of two steps imputations, calculate the DAS28-hsCRP based on the values of individual components in the 25 complete datasets and the same statistical analysis method described in the primary analysis will be conducted for each of the 25 completed datasets. The SAS procedure MIANALYZE will be used to combine the results for the statistical inferences.

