4.2.2 Handling of Withdrawals

Subjects who discontinue study treatment or active participation in the study will no longer receive study drug. When a subject withdraws from the study, the reason(s) for withdrawal shall be recorded by the investigator on the relevant page of the eCRF. Whenever possible, all subjects who discontinue study drug or withdraw from the study prematurely will undergo all end-of-study assessments.

Subject who choose to discontinue study drug treatment but continue to participate in the study should complete end of treatment visit as soon possible, preferably within 2 weeks. Afterwards, subjects should follow the regular visit schedule and adhere to all study procedures except for dispensing study drug and blood sample collection for optional exploratory research and validation studies.

Subjects who fail to return for final assessments will be contacted by the site in an attempt to have them comply with the protocol. Following a minimum of 2 documented unsuccessful telephone calls, a registered letter will be sent to the subject in a final attempt to ensure protocol compliance.

It is vital to obtain follow-up data on any subject withdrawn because of an AE or serious AE (SAE). In every case, efforts must be made to undertake protocol-specified, safety, follow-up procedures.

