4.2. Baseline Definition and Visit Window

Baseline value is defined as the last non-missing value on or before the date of the first dose of study drug. For subjects who were not treated, the baseline will be the assessment value taken on the screening visit, on or before the randomization day.

There is no separated visit folder designed in EDC for the treatment early terminated visit and the visit folder 'Visit 5 EOT' will serve as both the visit at Week 12 and the early terminated visit. Therefore, the assessments captured under visit folder 'Visit 5 EOT' will be summarized under visit Week 12 only when the subjects completed the treatment period; otherwise, 'Visit 5 EOT' will be treated as the treatment early terminated visit. There is no other visit mapping

performed and all the by-visit summaries will be based on the nominal visit as collected on the eCRF page except the visit handling of ‘Visit 5 EOT’.

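### The assessment made when a subject leaves early has no place in the multiple imputation or the MMRM, which weakens, but is not shown to break, their missing-at-random assumption

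*SAP*

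**What the plan says.** Protocol 4.2.2 has early leavers assessed on departure: "Whenever possible, all subjects who discontinue study drug or withdraw from the study prematurely will undergo all end-of-study assessments". In Protocol Table 6-1 the end-of-study assessments include the 28-joint counts and hsCRP, which are the three components of the primary score.

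SAP 4.2 explains that one EDC folder, Visit 5 EOT, serves both as Week 12 and as the early-termination visit. Its contents "will be summarized under visit Week 12 only when the subjects completed the treatment period"; for anyone else the folder "will be treated as the treatment early terminated visit". The section adds: "There is no other visit mapping".

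The models are then defined on scheduled visits:

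- **MI, SAP 8.2.3.** It will "impute the missing value for each individual component at the scheduled post-baseline analysis visits (up to Week 12". In the regression step, "The missing values at each visit will be imputed based on treatment, stratification factors", together with baseline and previous visits. MAR is named as the framework.
- **Central-laboratory analyses, SAP 8.2.4.** The MAR version reuses this MI. The control-based MNAR version shares its first step.
- **MMRM, SAP 8.3.1.** It is fitted "including all the scheduled visits up through Week 12". The specification reads: "The model will be fitted with treatment group, visit, treatment by visit interaction and baseline as fixed effects".

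No section brings the termination value back as an outcome or an auxiliary variable. The LOCF analysis (SAP 8.2.2) does not name the visits it may carry forward from.

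**The concern.** MAR is conditional on the data a model uses. A subject who leaves because of a flare may show that flare for the first time at the termination visit. If the value is left out, missingness depends on something measured but unused, and the absent Week 12 score is predicted from earlier, better visits. The arm with more such withdrawals then looks too good.

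The MI is one of the checks on the observed-case primary analysis. A check that ignores the last value of the subjects who left shares part of the weakness it is meant to probe. The MMRM is the main analysis for most of the continuous secondary endpoints. MAR is explicit for the MI and only implicit for the MMRM.

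**Working it through.** **1. The plan's own figure.** Inputs from SAP 4.3: difference 0.8, SD 1.25, alpha 0.05, 37 completers per group, one-way ANOVA. With one of four groups shifted by 0.8, the group means have sum of squares 3 × 0.2² + 0.6² = 0.48, so the noncentrality is 37 × 0.48 / 1.25² = 11.4. Power is 0.806 at 37 per group and 0.794 at 36, so 37 is reproduced. This point does not dispute it. The standard error of a pairwise difference, used as a yardstick below, is 1.25 × √(2/37) = 0.29.

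**2. How many subjects.** At the plan's 10% dropout, 0.10 × 148 = 14.8 and 0.10 × 168 = 16.8 (with the 20 extra subjects). That is 3.7 to 4.2 per arm. It is an upper bound, because the assessment is made only when possible and some of those lost to follow-up will have none.

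**3. Bias in one arm's Week 12 mean.** The documents give no visit correlations and no withdrawal mechanism, so these are assumptions: SD 1.25, correlation over 4 weeks of 0.70 to 0.85, and withdrawal logistic in the score at the termination visit. A single score was modelled by sequential regression in large samples. A negative value means the arm looks too good.

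| Dropout | Observed cases | Scheduled visits only |
|---|---|---|
| 5% | -0.04 to -0.08 | -0.01 to -0.02 |
| 10% | -0.07 to -0.15 | -0.01 to -0.04 |
| 20% | -0.14 to -0.27 | -0.03 to -0.07 |

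Even without the termination value, using the scheduled visits removes most of the observed-case bias.

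**4. Bias in the treatment difference.** It arises only as far as withdrawal differs between arms.

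- Large-sample check, same correlations: 0.00 with 10% in both arms, 0.03 with 15% placebo and 4% active, 0.05 with 25% and 8%.
- MMRM on 250 simulated trials per setting, 37 per arm, true difference -0.80, Monte Carlo SE about 0.017:

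| Withdrawal, placebo / active | Value omitted | Value used |
|---|---|---|
| 15% / 4% | -0.77 | -0.81 |
| 25% / 8% | -0.73 | -0.81 |

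Measured against the truth, the MMRM shortfall is 0.03 and 0.07. Measured against the fit that uses the value, it is 0.04 and 0.08. The overall range of 0.03 to 0.08 is 0.03/0.29 = 0.1 to 0.08/0.29 = 0.3 standard errors, toward no effect.

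**5. Candidate rules.** Bias in an arm mean on a weekly grid, with withdrawal slope 1 per DAS28 unit and ties sent to the empty visit:

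| Dropout | Omitted | Nearest visit, if empty | Next visit, unadjusted |
|---|---|---|---|
| 10% | -0.019 to -0.028 | +0.008 to +0.010 | +0.017 to +0.025 |
| 20% | -0.038 to -0.064 | +0.014 to +0.017 | +0.037 to +0.044 |

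The nearest-visit rule cuts the bias by about half or more. Moving the value unadjusted to the next visit only reverses its sign.

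The nearest-visit rule does not place every value. A subject seen on Day 56 who leaves on Days 57 to 69 is closest to Week 8, which already has a record. In one check, 41% to 47% of termination values stayed unassigned. That share depends on the assumed timing of withdrawal.

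**The case against.** Using nominal visits is a stated choice in SAP 4.2, not a contradiction. At the plan's own 10% dropout, spread evenly, the bias in the treatment difference is about zero. The non-zero figures need placebo withdrawal three to four times active, which nothing in the documents supports. The milder MMRM result is only (0.80 - 0.77)/0.017 = 1.8 Monte Carlo standard errors from no bias.

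The simulations also fall short of the planned methods. None ran the component-level MI. The MMRM used visit-specific baseline slopes, which SAP 8.3.1 does not specify, and it placed the termination value exactly on a nominal visit. All of this stands, and it limits the claim to direction and rough size.

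A reader might infer three stronger things:

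- **That the data are thrown away.** This holds for the MI and the MMRM only. Efficacy data are listed, and LOCF might use the value because SAP 8.2.2 is silent.
- **That MAR fails.** The documents give no withdrawal mechanism, so MAR is harder to satisfy, not refuted. SAP 8.2.4 also has a control-based MNAR analysis, though only within the central-laboratory hsCRP analysis.
- **That the primary result is affected.** The primary analysis is an observed-case ANCOVA at Week 12 and does not use these values by design.

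The objection does not remove the gap itself: a measured and relevant value has no route into two analyses that lean on MAR, and a short rule would give it one.

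**Conclusion.** The point holds in a limited form. SAP 4.2, read with 8.2.3, 8.2.4 and 8.3.1, leaves the termination joint counts and hsCRP out of the MI and the MMRM. This weakens MAR for a sensitivity analysis of the primary endpoint and for the secondary-endpoint model.

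The expected effect is small: hundredths of a DAS28 unit in an arm mean at the planned dropout, and at most about 0.3 standard errors in the difference under strongly unequal withdrawal. Both rest on an assumed correlation and on withdrawal driven by the score at departure. It is worth correcting because the data will already be in the database and the rule is cheap, not because it threatens the trial's conclusion.

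**What to change.** Before database lock, add one rule to SAP 4.2 and refer to it in 8.2.3, 8.2.4 and 8.3.1:

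- Assign an early-termination assessment to the nearest scheduled visit by study day when that visit has no record, and state how ties are resolved (for example Day 70, midway between Days 56 and 84).
- Use the assigned value in the MI, as outcome and predictor, and in the MMRM.
- When the nearest visit already has a record, do not move the value unadjusted to the next visit. Use it as an auxiliary predictor in the MI.
- In SAP 8.2.2, state whether LOCF may carry the termination value forward.
- Leave the observed-case Week 12 ANCOVA as it is.

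The cost is one derivation in the analysis data set and a few lines of SAP text. The small downside is that some values will lie off the nominal day.
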